c) Name/number of the model/type, software version and accessories

to hand in later

d) Description of traceability during and after the clinical investigation

to hand in later

e) Intended purpose

alivis is intended to provide therapeutic methods and exercises based on evidence-based psychological and psychotherapeutic therapies for patients with

BPD, to help them manage their BPD symptoms. *alivis* is intended as a self-application for patients 18 years of age or older. *alivis* is neither intended to replace treatment provided by a health care provider nor to provide information which is used to make decisions with diagnosis or therapeutic purposes.

f) Populations and indications

Patients with Borderline Personality Disorder, ICD-10: F60.31 /ICD-11: 6D10.

g) Description of the investigational device

alivis is an interactive online program for independent use by users with BPD. It focuses on recognized treatment elements from DBT, ST, ACT, and MSC.

The program *alivis* is based on proprietary software of the developing company (broca®), with access via password-protected and https-encrypted websites. The program can be used on conventional web-browsers on desktop PCs, tablets and smartphones. Users (patients randomized to the intervention group) receive access to the program for 12 months by 12-digit personal codes (vouchers), provided by the developer. Data protection and data security will be ensured by compliance with legal regulation. After initial registration and consent of general terms and conditions, users can log into the program using their email address and personal password at any time. The program is set up as an adaptive- and responsive-web-design pulling a layout template for a specific device, adapting to dimension and resolution of the display used. This results in high flexibility of usage regardless of the available hardware.

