- Questionnaire on treatment satisfaction (ZUF-8; 50)
- subjective improvement of BPD symptoms and quality of life

Exploratory Variables:

- Modified version of Working Alliance Inventory WAI-I (51)

Usage monitoring (It should be noted that these data reflect only measurable engagement with *alivis* itself and do not capture how long a person has engaged with its content outside *alivis*, e.g. short text messages sent by *alivis* or PDF-materials printed from *alivis*):

- Number of chats completed
- Number of days active
- Time spent in the program

Safety and usage monitoring:

- Negative Effects Questionnaire (NEQ; (52))
- Respective user feedback via email, telephone or contact form on the *alivis* trial website
- Suicide attempts (T0-T2: past 3 months, T3: past 6 months; main safety outcome)
- other life-threatening events (e.g., non-suicidal self-injury, drug intoxication, accidents)
- Unplanned and emergency outpatient and inpatient treatments (T0-T2: past 3 months, T3: past 6 months)
- Monitoring of adverse events throughout the trial (serious adverse events will be reviewed by a Safety Officer/ PRRC)
- Usage

d) Methods and timing

Severity of Borderline Symptoms

~~The total score of the Borderline Symptoms List 23 (BSL 23)~~

~~The BSL 23 is a 23-item PROM with good psychometric properties that was validated and tested for reliability in a representative German sample (test-retest reliability $r = .82$, $p < 0.0001$; $\alpha = 0.94-0.97$; high correlation of total score with general psychological burden and depression (53)) to assess the typical symptomatology and severity of BPD (54). It refers to the last week and has a range from 0 = “not at all” to 4 = “very strong”. Its single factor structure was optimized to reflect levels and changes in severity of BPD-symptomatology based on a mean score (32).~~

~~Responders will be defined by a change of borderline symptom severity on the BSL 23 total score following both conditions: (i) reaching the psychometric criterion of a reliable change index (RCI) (33) and (ii) a change of BSL-23 total score towards a less severe grade from T0 to T1. Deteriorators will be defined accordingly by both, (i) reaching RCI and (ii) a change of BSL 23 total score towards a more severe grade from T0 to T1. Non-responders will be defined as no change of the borderline severity grade, even if the RCI was reached.~~

Depression

~~Total score of Patient Health Questionnaire (PHQ 9)~~

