The PAM13 assesses patients' active participation in their medical care using 13 items (43,44). Items are answered using a Likert scale ranging from 1 = "strongly disagree" to 4 = "agree strongly", yielding a total score between 13 and 52. The German version of the PAM13, the PAM13-G, is validated and demonstrates good psychometric properties, including a good internal consistency of Cronbach's $\alpha = 0.84$ (44). An improvement of 4 points on the PAM-13 is considered an MCID (56). Therefore, responders will be defined as patients who improve by at least 4 points on the PAM-13 from T0 to T2. The proportion of responders between groups will be compared using χ^2 tests.

Table 1| Chronological Sequence of the Trial

	Recruitment	Allocation	Post Allocation	Follow-up
Timepoint	T0		T1	T2, T3
Screening				
Test of Inclusion Criteria	x			
Test of Exclusion Criteria	x			
Sociodemographic Variables	x			
Clinical Variables	x		x	x
Consent	x			
Randomization		x		
Intervention				
Intervention group: alivis + TAU		♦	♦	♦
Control group: TAU + publicly available information material on BPD				
Endpoints				
BPD symptom severity (BSL-23)	x		x	x
Depression (PHQ-9)	x		x	x
General Anxiety (GAD-7)	x		x	x
Costs questionnaire	x		x	x
Social Functioning (WSAS)	x		x	x

Health-Related Quality of life (AQoL-8D)	x	x	x
BPD symptom severity (BPD-GL)	*	*	*
Patient activation (PAM-13)	x	x	x
Clinical Course	x	x	x
Net Promoter Score (NPS)*		x	x
Subjective improvement		x	x
Usage of the Program*		x	x
Exploratory Variables	x	x	x
Adverse Events (incl. NEQ)		x	x

T0: Before start of Intervention (baseline), T1: 3 months post allocation, Follow-up: T2: 6 months post allocation, T3 = 12 months post allocation. Black diamonds indicate access to *alivis*. *only assessed in the intervention group.

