6.5 Monitoring plan

Documented monitoring visits will be conducted before, during (twice) and after the trial (close-out visit) by the sponsor to ensure adherence to the study protocol. The following items will be monitored during the audits: (i) presence of approval by ethical review board, (ii) qualification of investigators, (iii) current status of recruitment and participant flow, (iv) adherence to study protocol (e.g., presence of informed consent, correct application of inclusion and exclusion criteria, allocation to correct intervention, usage of intervention) and (v) correctness of data entries and consistency with the source documents.

7. Statistical design and analysis

All analyses and imputation procedures will be performed using standard statistical software such as *R* (59) or *SPSS*.

a) Analysis population

In line with recommendations of the CONSORT eHealth statement, we will conduct both intention-to-treat (ITT) and per-protocol (PP) analyses (60–62). For PP-analyses, the dataset will be filtered based on the variable “usage time”. Individuals in the intervention group who did not use *alivis* for at least 4 times on 4 different days will be excluded from the PP dataset. Additionally, we will exclude participants from both groups who reported using other digital health interventions for BPD for the relevant follow-up period.

b) Descriptive statistics of baseline data, treatments, safety data

Descriptive statistics will include mean value and standard deviation (or median, min, max and quartiles as appropriate) for continuous data and absolute numbers and percentages for categorical data. These will be presented separately for the intervention and control group at baseline.

c) Analytical procedures and measures of precision

The Principal Investigator will receive access to all data prior to analysis and will remain blinded to group assignment until the end of the analysis of the primary outcome and main safety outcome (suicide attempts).

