Analysis of effectiveness of the intervention in addition to TAU vs. TAU will be performed by ANCOVA of the primary endpoint and all secondary endpoints (tested in sequential order in a gatekeeping testing strategy, see section 7. k), in which the posttreatment scores at T1 will be compared between treatment groups (intervention group vs. control group), using the baseline scores of the respective outcome as a covariate. Treatment effects, i.e., the difference in posttreatment scores, will be reported on the original scale, along with the 95%-CI. In addition, Cohen's *d* (calculated as between-group difference divided by the pooled standard deviation) will be used as a standardized effect size to quantify differences in posttreatment outcomes. Tests of prolonged treatment effects at T2 and T3 will be performed analogously with baseline as covariate. The ITT analyses will comprise all randomized participants, with imputed outcome values as described in section 7. m.

Analysis of binary or count outcomes (such as medication or number of hospitalizations) will be conducted based on non-responder imputed data in the form of χ^2 -tests and Poisson regression, as appropriate, to examine between-group effects at T1, and analogously for T2 and T3.

The primary analysis will be performed as an ITT analysis with multiple imputation under ‘missing at random’ (MAR) assumption. In addition, a conservative sensitivity analysis based on reference-based multiple imputation (J2R imputation) will be calculated (63).

An exploratory PP analysis will be conducted (61,62). For PP analyses, the dataset will be filtered based on the variable “usage time”. Individuals in the intervention group who did not use *alivis* for at least 4 times on 4 different days will be excluded

from the PP dataset (62). Additionally, we will exclude participants from both groups who reported using other digital health interventions (e.g., DiGAs, apps, online programs) for BPD for the relevant follow-up period.

Measures of accuracy will be p -value [significance level (α) < 0.05] and the corresponding 95% confidence interval.

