Moreover, responder analyses will be conducted. Unless a specific MCID is specified for an endpoint in section 6.1d), responders will be defined by reaching the cut-off of 15% of the range of the scale (64). ~~the reliable change index (RCI; 33) will be used to identify responders to treatment in patients with complete observations. The RCI is calculated as the ratio of the difference between pre- and post-scores of an individual participant (numerator) and the standard error of measurement of the difference (denominator). RCI scores larger than 1.96 indicate that it is unlikely that the posttest score is not reflecting real change ($p < .05$), thus indicating that the participant is a responder (33).~~ If a specific MCID is specified for an endpoint, responder analyses will instead be based on that value. Responders will then be defined as participants reaching this difference from T0 to T1. Additionally, exploratory responder analyses will be conducted for each endpoint, where response is defined as 50% improvement since baseline. The proportion of responders between groups will be compared using χ^2 tests. Moreover, the odds ratio will be reported.

d) Significance level and power

significance level (α) = 0.05 (two-sided)
power = 0.80

e) Sample size

1) Clinical data on outcome variable and effect size

An effect of Cohen's $d = 0.27$ has been observed for a digital intervention for BPD that is based on ST only (27). Given that *alivis* consists of a combination of DBT, ST, ACT, and MSC and that participants will be closely guided during the trial, we expect the observed effect to be slightly larger and assume an effect size of $d = 0.30$. In order to obtain a power of 0.80, at a two-sided significance level of 0.05, each group should have a sample size of 176. Outpatient RCTs for BPD have an average dropout rate of approximately 25% (28,29). To compensate for dropouts, we thus aim to include and randomize $N = 470$ (2×235) participants with an allocation ratio of 1:1.

2) Expected outcomes across treatment groups

See 5. d.

3) Adjustments due to pre-planned interim analyses

An interim analysis is planned after three months (T1; primary time point). There will be no adjustments.

4) Effect size and non-inferiority margin

See 7. e 1).

5) Randomization allocation ratio

1:1, in variable blocks of 4, 8, or 16 participants each ~~no block randomization, no stratification~~

6) Expected drop-out rate

25% (28,29).

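### No full-period comparison of suicide attempts, the main safety outcome, is specified; the only rule that fits compares T1, T2 and T3 separately, and each test has low power unless attempts are common

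*Combined protocol and SAP*

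**What the plan says.** - **Outcome and windows.** Section 6.1 c), under safety and usage monitoring: "Suicide attempts (T0-T2: past 3 months, T3: past 6 months; main safety outcome". After baseline, T1 covers months 0-3, T2 months 3-6 and T3 months 6-12.
- **Exposure.** Section 2.g: users in the intervention group "receive access to the program for 12 months". The same section and 6.2 a) give controls access only after 12 months, so the randomised contrast holds for the whole year.
- **A formal analysis is intended.** Section 7.c keeps the principal investigator blinded "until the end of the analysis of the primary outcome and main safety outcome (suicide attempts". It does not say over which window.
- **The only rule that fits.** Section 7.c: "Analysis of binary or count outcomes (such as medication or number of hospitalizations) will be conducted based on non-responder imputed data", by χ² tests or Poisson regression, "to examine between-group effects at T1, and analogously for T2 and T3". Suicide attempts are not among the examples given.
- **Error rate and sample size.** Section 7.d: "significance level (α) = 0.05 (two-sided". Section 7.e sizes the trial on BSL-23 alone ("assume an effect size of $d = 0.30"). It gives no attempt rate, harm margin or power for the safety outcome.
- **Baseline.** Section 6.1 c) collects attempts at T0, and 14.a says they are asked about at every measurement time. In Table 1 the row "Adverse Events (incl. NEQ" is marked only after allocation.

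**The concern.** The natural safety question for a 12-month exposure is whether more people in one arm attempted suicide during those 12 months. As written, each comparison of the main safety outcome uses a quarter or a half of that period. No analysis adds the windows up, although together they cover the year without a gap. The plan also does not say which window is the main safety analysis. The blinding rule in 7.c, together with the first analysis after the last T1 (6.1 d and 7.h), suggests the 0-3 month result, which is one of the two weakest.

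What is at stake is interpretation. Three separate tests of a rare event, with no rule for reading one positive among three, can be reported as no difference when the data are merely sparse, or as a signal when one window is extreme by chance. Non-responder imputation adds to this. It has no evident meaning for a harm outcome: coding a missed survey as an attempt or as no attempt changes the rates in both arms.

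**Working it through.** **The plan's own figure (BSL-23).** The normal approximation gives n = 2(1.960 + 0.842)²/0.30² ≈ 174.4, so 175. The t-test version gives 175.4, so 176. Then 176/0.75 = 234.7, so 235 per arm. The stated sample size reproduces, but it says nothing about suicide attempts.

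**Inputs.** From the documents: 235 per arm randomised, 176 per arm after 25% dropout, two-sided 5% level, windows of 0.25, 0.25 and 0.5 years. Assumed, because the documents are silent: 12-month control risk p of 5, 10 or 15%; constant hazard; alivis doubles it; uncorrected χ² test; complete data at the stated n.

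**Formulas.** Hazard h = -ln(1-p). Control risk in a window of w years = 1-exp(-hw); alivis risk = 1-exp(-2hw). Power ≈ Φ{[(p₂-p₁)√n - 1.96√(2p̄(1-p̄))]/√(p₁(1-p₁)+p₂(1-p₂))}.

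**Worked case, p = 10%, n = 235** (√n = 15.33).
- T1: 2.60% against 5.13%. (0.388 - 0.534)/0.272 = -0.54, power about 0.29.
- Twelve months: 10% against 19%. (1.380 - 0.976)/0.494 = 0.82, power about 0.79.

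**Power to find a doubling in the harm direction** (simulation of 20,000 trials; the formula agrees within about 0.02).

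| 12-month control risk | 5% | 10% | 15% |
|---|---|---|---|
| 235 per arm: T1 or T2 | 0.15 | 0.29 | 0.42 |
| 235: T3 | 0.29 | 0.52 | 0.71 |
| 235: at least one of the three | 0.49 | 0.76 | 0.90 |
| 235: cumulative, 0-12 months | 0.50 | 0.80 | 0.93 |
| 176 per arm: T1 or T2 | 0.12 | 0.23 | 0.33 |
| 176: T3 | 0.22 | 0.41 | 0.57 |
| 176: at least one of the three | 0.40 | 0.65 | 0.81 |
| 176: cumulative, 0-12 months | 0.40 | 0.68 | 0.84 |

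The third row follows from the first two. At 10%, 1 - 0.71 × 0.71 × 0.48 = 0.76.

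**Price of reading three tests.** If the tests are independent, the chance of at least one false positive is up to 1 - 0.95³ = 0.14 two-sided. At 10% control risk, two or more windows agree on harm in only about 0.3 of trials (235 per arm) or 0.19 (176).

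**If risk varies strongly between people** (gamma frailty, shape 0.5; 235 per arm), some people have events in several windows and cumulation gains less.
- 3-month control risk 2%: cumulative 0.58, at least one hit 0.61, T3 alone 0.37.
- 3-month control risk 5%: cumulative 0.78, at least one hit 0.85, T3 alone 0.64.

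**If the doubling is confined to months 0-3** (10% control risk, 235 per arm), the 12-month alivis risk is 1-exp(-0.10536 × 1.25) = 12.3% against 10%. Cumulative power is then about 0.12 to 0.13, while T1 keeps 0.29.

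**The case against.** A reader might infer that a real doubling would probably be missed in every analysis. The documents do not support that, because it depends on a control rate they do not give. With 235 per arm, all three tests miss with probability 0.51, 0.24 and 0.10 at 5, 10 and 15%. At 5% the cumulative test misses about as often, so rarity and sample size are the limit there, not the splitting of windows. This objection stands.

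A full-period analysis can also hide early harm. Section 6.1 expects the relevant content to be covered within three months and use to be highest in the first months. If harm followed that pattern, T1 would be the more sensitive test. This stands too, and it is why the 0-3 month comparison should not be demoted.

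The plan is silent on a cumulative analysis and does not exclude one, and 7.c does not name suicide attempts. That is fair, but no other rule is offered, and the silence is what needs filling. Adverse events are also monitored throughout, with serious ones reviewed by a safety officer or the PRRC (6.1 c), so detection does not rest on these tests alone. That does not replace an arm comparison. There is no DMC (14.j), the serious-event definition in 14.c requires at least a likely causal link to the device, and 14.a gives the intervention group an additional reporting channel.

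Two further inferences fail. The benefit-risk statement in 4.f is a prospective rationale and does not rest on these tests. The blank T0 cell in Table 1 does not show that baseline attempts would be lost, since 6.1 c) and 14.a both state collection at T0.

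**Conclusion.** The point holds as a gap in specification. The main safety outcome has adjoining windows over the full randomised period, but no full-period comparison, no named primary window, and no workable missing-data rule. Each test taken singly has low power for a doubling unless attempts are common: T1 or T2 stays below 0.5 throughout the assumed range of 5 to 15% over 12 months.

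The benefit of cumulating is moderate. It clearly beats any single window when the hazard ratio is constant (0.80 against 0.29 and 0.52 at 10% with 235 per arm). Against the chance of any hit across three unadjusted tests it adds at most a few hundredths, and with strong variation between people it can fall slightly below. Its main value is one estimate with an interval, at a 5% error rate, that answers the question for the whole exposure. At low attempt rates neither approach has good power, which makes the interval matter more than the test.

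All power figures rest on the assumed control rates and a doubled hazard; the main table also takes the hazard as constant and the data as complete. The Table 1 discrepancy is clerical.

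**What to change.** - In 7.c, prespecify a comparison by arm of any suicide attempt from randomisation to T3, combining the T1, T2 and T3 reports, with risk difference and risk ratio and 95% confidence intervals, adjusted for any attempt at T0 where feasible.
- Keep the 0-3 month comparison alongside it with equal visibility, because early harm would be diluted in the 12-month result.
- For this outcome, replace non-responder imputation with a rule suited to harm, for example analysis of observed follow-up time plus a sensitivity analysis for missed surveys.
- Say in 7.c that suicide attempts fall under this rule, and report the detectable risk ratio over a range of control rates.
- Reconcile the T0 cell of Table 1 with 6.1 c) and 14.a.

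The cost is analysis-plan wording and one table entry, with no new items, visits or participants. The downsides are that the cumulative result comes only after T3, and that participants who miss surveys contribute partial follow-up.

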complete an online questionnaire. Although participants receive access to *alivis* for 12 months, we expect highest usage of the intervention during the first months, as was the case for our intervention *priovi* (27; as well as still unpublished data from a follow-up RCT). Effects of *alivis* should therefore already be seen after three months. Additionally, patients will be surveyed after six and 12 months (T2 and T3; evaluating stability of effects). As an incentive, participants will receive a 10€ voucher from www.wunschgutschein.de per assessment (T1, T2, and T3; maximum $3 \times 10\text{€} = 30\text{€}$). All participants (from the intervention and control group) will receive this compensation if they complete the questionnaires and interview, and, in particular, the compensation in the intervention group will not depend on the actual use of *alivis*.

Contact to the participants will be established by a study director. Technical and content support for the intervention is offered via a central hotline, which is managed by a staff member who is not involved in the evaluation of the study. Participants in the intervention group will be contacted by email and/or phone if they have not redeemed their voucher for access to *alivis* 7 days after randomization. For a flow chart of the trial design, see Figure 1.

The present RCT is designed to compare *alivis* in addition to TAU with TAU only. The required initial interview to confirm diagnosis of BPD maximizes the probability that *alivis* will be tested in the appropriate intended target group.

[figure not shown]

Figure 1| Flow Chart of Trial Design

The primary time point for analysis of effectiveness of the intervention will be three months after inclusion (T1). Other timepoints of data acquisition: T2 (Follow-up) = six months after inclusion, T3 (Follow-up) = 12 months after inclusion.

a) Description of the design type of clinical investigation to be performed

- prospective
- randomized (simple randomization, 1:1, in variable blocks of 4, 8, or 16 participants each)
- two arms
- controlled (against TAU)

- online (no traditional investigation site)

b) Measures against bias

After successful screening of inclusion and exclusion criteria participants will automatically be randomized to one of two study groups (control group or intervention group) based on an algorithm.

c) Primary and secondary endpoints

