~~Severity of borderline symptoms at T1, assessed via the Borderline Personality Disorder Checklist (BPD-CL).~~

~~The BPD-CL is a DSM-IV based self-report instrument to assess BPD symptoms in the previous month (42). Importantly, in contrast to the BSL-23, the BPD-CL explicitly assesses all nine DSM-5 criteria.~~

Patient activation at T1, assessed via the Patient Activation Measure (PAM-13)

The PAM13 assesses patients' active participation in their medical care using 13 items (43,44). Items are answered using a Likert scale ranging from 1 = "strongly disagree" to 4 = "agree strongly", yielding a total score between 13 and 52. The German version of the PAM13, the PAM13-G, is validated and demonstrates good psychometric properties, including a good internal consistency of Cronbach's $\alpha = 0.84$ (44). An improvement of 4 points on the PAM-13 is considered an MCID (56). Therefore, responders will be defined as patients who improve by at least 4 points on the PAM-13 from T0 to T2. The proportion of responders between groups will be compared using χ^2 tests.

~~The PAM-13 is a 13-item instrument assessing patients' active participation in their medical care (43). The German version of the PAM-13, the PAM-13-G, is validated and demonstrates good psychometric properties (44).~~

Exploratory Endpoints: Assessments listed in "Secondary endpoints" at T2/T3

Sociodemographic Variables:

- Age
- Gender

- Sex
- Education
- Employment Status
- Family Situation
- Language ability
- Ethnicity

Clinical Variables:

Assessed at T0 only:

- First diagnosis (date)
- Inclusion diagnosis (BPD) using the respective section of the SCID-5-PD interview (45)
- Psychiatric comorbidities (via Mini-DIPS) (46)
- Psychotherapy (past, type)

Assessed at all timepoints (T0-T3):

- Medications (name of medication, dose, frequency)
- Psychotherapy (current, type)
- Childhood trauma (via Childhood Trauma Questionnaire (CTQ; 47,48))
- Number of BPD-related hospitalizations (T0: past 12 months, T1-T2: past 3 months, T3: past 6 months)
- Number of hospitalizations due to other reasons (T0: past 12 months, T1-T2: past 3 months, T3: past 6 months)
- Number of days in sick leave (past 3 months)
- Number of days in sick pay (past 3 months)
- weight and height (current)
- Use of any other online program for BPD (T0: lifetime, T1-T2: past 3 months, T3: past 6 months; name)

Treatment satisfaction:

- Program Evaluation of the Program (NPS, Net Promoter Score) (49)

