6.3 Subjects

a) Inclusion criteria

- male, female, non-binary
- age 18-65
- diagnosis of BPD (telephone interview via SCID-5-PD (45))
- borderline severity score (cut-off) of ≥ 1.07 on the BSL-23
- Stable treatment (e.g., psychotherapy, medication, no treatment,---) for at least 30 days at the time of inclusion
- consent to emergency plan for suicidal crises
- consent to participation
- sufficient knowledge of the German language

b) Exclusion criteria

- Plans to change ~~in~~-treatment (e.g., psychotherapy, medication,---) in the upcoming 3 months after inclusion
- Comorbid diagnosis of substance use disorder
- Lifetime diagnosis of psychotic disorder like schizophrenia or schizoaffective disorder (except non-transitory paranoid ideas that can be concomitant with BPS and in which the ability to test reality is mostly preserved)
- Diagnosis of a physical condition that can cause serious psychiatric symptoms
- Acute decompensation of mental health symptoms, e.g. acute manic state or acute suicidality
- BMI <15
- current psychiatric day-care or inpatient treatment
- Prior use of *priovi*

c) Criteria and procedures for subject withdrawal or lost to follow-up

1) Withdrawal of a subject or stop of use

Participants will be informed of their right to withdraw from the study at any time without negative consequences. Test subjects will not be included in the clinical trial (not randomized) if it was not possible to ascertain baseline variables (T0). There is no provision for withdrawal of follow-up examinations.

2) Tracing of subjects lost to follow-up

At prespecified points in the course of the study, participants whose response to a survey is still outstanding will be reminded by email and/or phone.

Subsequent replacement of test subjects who evade follow-up examinations is not intended. Missing data points will be imputed by applying multiple imputation (cf. section 7. m). Possible reasons for being lost to follow-up include but are not limited to no further need for a treatment (known as “good enough effect” (57,58)), lack of positive effects of the treatment, or loss of interest among control group participants.

3) Replacement of subjects

Following standards for RCTs there will be no replacement of participants.

d) Point of enrolment

With randomization and allocation to a study group the participants are enrolled in the trial.

e) Point of randomization

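### The recall windows for suicide attempts and related survey items are not tied to allocation or to the last completed survey, so a skipped or late survey leaves time that no question covers

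*Combined protocol and SAP*

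**What the plan says.** Table 1 in section 6.1 d) places T1, T2 and T3 at 3, 6 and 12 months after allocation. Section 6.1 c) sets the recall windows:

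- Main safety outcome: "Suicide attempts (T0-T2: past 3 months, T3: past 6 months; main safety outcome".
- Emergency care: "Unplanned and emergency outpatient and inpatient treatments (T0-T2: past 3 months, T3: past 6 months".
- Hospital stays: "Number of BPD-related hospitalizations (T0: past 12 months, T1-T2: past 3 months, T3: past 6 months". The item on stays for other reasons has the same windows.
- Sick leave and sick pay, under the heading "Assessed at all timepoints (T0-T3": "Number of days in sick leave (past 3 months" and "Number of days in sick pay (past 3 months", with no longer window at T3.

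On late answers, section 6.3 c) 2) says that "participants whose response to a survey is still outstanding will be reminded by email and/or phone". Section 6.1 h) allows up to a month of reminders for T3. No closing date is given for T1 or T2. No section widens a window, or ties it to the last answered survey, when a survey is skipped or late.

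**The concern.** Each window equals the planned spacing between surveys, so there is no slack. Any departure from the schedule opens a hole, an overlap or both in the structured question on the main safety outcome. The first weeks are the most exposed, because a late T1 drops the start of follow-up. That is when the sponsor says "we expect highest usage of the intervention during the first months".

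Suicide attempts can be expected to be few, so a handful of unasked or doubly reported events could change the comparison between arms. Section 7 c) assigns count outcomes to Poisson regression and says nothing about the time each person's answers cover.

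**Working it through.** **Inputs.** Survey months 3, 6 and 12 (Table 1). Windows of 3, 3 and 6 months for suicide attempts, emergency treatment and hospitalisations, and 3, 3 and 3 months for sick leave and sick pay (section 6.1 c). The one-month delay is the T3 buffer from section 6.1 h). Applying it to T1 and T2 is an assumption.

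**Rule.** A survey answered at month t with window w covers t − w to t.

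**Planned schedule, 3/3/6 windows.** T1 covers 3 − 3 = 0 to 3, T2 covers 6 − 3 = 3 to 6, and T3 covers 12 − 6 = 6 to 12. Nothing is uncovered and nothing overlaps, so the design works as intended when every answer is on time.

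**Departures, 3/3/6 windows**

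| Scenario | Months not asked about | Months asked about twice |
|---|---|---|
| T1 skipped | 0-3 | none |
| T2 skipped | 3-6 | none |
| T1 and T2 skipped | 0-6 | none |
| T1 half a month late (3.5) | 0-0.5 | 3-3.5 |
| T1 one month late (4) | 0-1 | 3-4 |
| T2 one month late (7) | 3-4 | 6-7 |
| T1 and T2 one month late | 0-1 | 6-7 |
| T3 one month late (13) | 6-7 | none |

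For example, T1 at month 4 covers 4 − 3 = 1 to 4, while an on-time T2 covers 3 to 6. A delay of half a month leaves 0.5/3 = 17% of the first three months unasked, and a delay of one month leaves 1/3 = 33%. A person who skips T1 but answers the later surveys has 3/12 = 25% of the year unasked.

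**Sick leave and sick pay, 3/3/3 windows.** On time, the items cover 0-3, 3-6 and 12 − 3 = 9 to 12. Months 6-9 are uncovered, which is 3/12 = 25% of the year. If T3 is one month late, the hole is 6-10. If T2 is one month late, that stretch shrinks to 7-9 but months 3-4 open up. A one-month delay never closes the gap.

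**Could another item fill the hole?** The emergency-treatment and hospitalisation questions share the windows at T1 to T3, so they miss the same time. The item on other life-threatening events has no stated window.

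**Trial-level scale, as a what-if only.** If a share q skips T1, the same share skips T2, and T3 is answered, the unasked part of the 12 months is 2 × q × 3/12 = q/2. An assumed q of 5% gives 2.5%, and 10% gives 5%. The documents offer no basis for choosing q.

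**With anchored questions.** If each survey asks about the time since the last completed one (since allocation at T1), uncovered time is zero in every row above. A missing T3 after an answered T2 would still leave months 6-12 open.

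**The case against.** **Other routes of capture.** Section 4 e) tells users to report adverse events through several channels. Section 14 a) counts suicide attempts among adverse events and has the study manager merge all sources. A reader might infer that attempts in an unasked period are lost to the trial. The documents do not support that: what is missing is the structured question. But these routes depend on the participant coming forward, the intervention arm has an additional one through the programme operator, and nothing says that such reports enter the main safety outcome.

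**Non-response is already managed.** Reminders, and vouchers at T1, T2 and T3, should limit it. That is fair, but reminders also produce late answers, which fixed windows handle badly.

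**Analysis is per timepoint.** Section 7 c) compares arms at T1 and then analogously at T2 and T3, and no cumulative 12-month count is defined. Fixed windows give every respondent equal exposure at each timepoint, whereas anchored questions would not. This is the strongest argument, and it would stand against anchoring alone. It falls away if the month of each event is recorded, because the planned fixed-window counts can then still be derived. The imputation of missing binary and count data in section 7 c) gives no rule for a safety event in an unasked period.

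**A constant 3-month sick-leave window is a repeated snapshot.** It keeps T3 comparable with baseline. That is defensible, though other items in the same list move to 6 months at T3 and no reason is given for the difference.

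**Conclusion.** The gap follows from the plan's own windows and survey months. It is absent when all surveys are answered on time and appears with any skipped or late T1 or T2, or a late T3. Skips leave 3 to 6 months unasked per person. A one-month delay leaves one month unasked and, for T1 or T2, can also create a one-month overlap with the next survey. Only the length of the delay at T1 and T2 is assumed.

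Three stronger readings are tempting and not supported:

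- *That the expected 25% dropout gives a number of participants with a gap.* In section 7 e) it is an average from other trials, used to raise 176 to 176/0.75 = 234.7, rounded to 235 per group. It is not a rate of skipping T1 and returning later, and permanent dropouts would not be recovered by any window.
- *That the safety comparison is biased between arms.* Participants know their allocation, and section 6.3 c) 2) names reasons for loss that could differ by arm, including waning interest in the control group. Differential loss is therefore possible, but nothing establishes its presence or size.
- *That the sick-leave gap damages the cost endpoint.* Costs come from a separate self-compiled instrument with no stated recall window (section 6.1 c) and are confirmatory at T1 only (section 5 d). The gap is shown only for the clinical-variable items on sick-leave and sick-pay days, and it is the lesser part of this point.

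**What to change.** 1. For suicide attempts, emergency treatment and hospitalisations, ask at T1 *since [allocation date]*. At T2 and T3 ask *since your last completed survey on [date]*, or since allocation if there was none. LimeSurvey inserts the date.
2. Record the month of each reported event. The fixed-window counts per timepoint can then still be derived, double reports removed, and events from a skipped period placed where they belong.
3. In any cumulative count analysis, use each person's covered time as an offset.
4. Set the T3 window for sick-leave and sick-pay days to 6 months. Alternatively, add months 6-9 as a separate item so that the 3-month value stays comparable with baseline.

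The cost is survey programming and wording for single items whose windows the sponsor set. Participants who skipped a survey face longer recall, and wording will be mixed if some surveys have already gone out.
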